## Clinical Protocol FIH-3

Doc No: CLINP1837  
Revision: D  
DCO No: 25-009  
Effective Date: 02/06/25

embolism, major thrombosis, major thromboembolism, major hemolysis, or major thrombocytopenia; local infection

- Amplifi System-related re-hospitalization or prolonged hospitalization;
- Amplifi System-related major surgery or major interventional procedure; or
- any Amplifi System-related complication determined to be an Amplifi System-related major complication by both an Investigator and the Medical Monitor.

\*Detailed definition of Major Device-Related Adverse Events is described in **Attachment 1: Definitions**

- **Rate of Occurrence of Cannulation-related Complications** [Timeframe: from AVF creation through end of follow-up period]

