## Appendix 1: Definitions

- *Abandonment of Study AVF* is defined as the discontinuation of the clinical use of Study AVF because it is no longer functional and considered not to be salvageable, including the discontinuation of the clinical use of Study AVF because it can no longer be used for prescribed hemodialysis, because it is unable to provide adequate blood flow, or because it is deemed unsafe for the patient, and the associated problem(s) cannot be corrected by any medical, procedural, or surgical intervention.
- *Amplifi System and AVF local infection* is defined as: 1) the presence of purulent discharge from the Inflow Catheter skin exit site, the Distal Outflow Catheter skin exit site, or the Study AVF skin incision; or 2) the presence of serous discharge from the Inflow Catheter skin exit site, the Distal Outflow Catheter skin exit site, or the Study AVF skin incision with erythema, induration, or tenderness and a positive culture of the serous discharge.
- *Amplifi System component replacement* is defined as the replacement of one or more components of the Amplifi System during the Amplifi System treatment period, not including replacement or addition of Access Port caps, suture anchoring tools, a Patient Vest, or Patient Vest components.
- *Amplifi System-related major complication* is defined as:
  - Amplifi System-related death;
  - Amplifi System-related major bleeding, major pneumothorax, major air embolism, major thrombosis, major thromboembolism, major hemolysis, or major thrombocytopenia; local infection
  - Amplifi System-related re-hospitalization or prolonged hospitalization;
  - Amplifi System-related major surgery or major interventional procedure; or
  - any Amplifi System-related complication determined to be an Amplifi System-related major complication by both an Investigator and the CEC.
- *Amplifi System-related major bleeding* is defined as:
  - overt bleeding plus a drop in hemoglobin of 3 to 5 g/dL wherein the hemoglobin drop is related to the bleeding;
  - transfusion for overt bleeding;
  - bleeding requiring an interventional procedure or surgery for control (not including the placement or removal of skin sutures or pressure dressings);
  - the administration of intravenous vasoactive agents for overt bleeding; or
  - probable or definite fatal bleeding.

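### The hemoglobin criterion for major bleeding stops at a 5 g/dL drop, so a larger drop can fall outside the major-bleeding component

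*Protocol*

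**What the plan says.** Major bleeding is a named component of the composite safety measure, the rate of major device-related adverse events (Synopsis, Safety Measures; Section 4.5). Section 4.5 sends the reader to the definitions for the details: "Detailed definition of Major Device-Related Adverse Events is described in" the definitions attachment, which is Appendix 1.

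Appendix 1 lists five criteria for major bleeding, any one of which is enough:

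- Hemoglobin: "overt bleeding plus a drop in hemoglobin of 3 to 5 g/dL wherein the hemoglobin drop is related to the bleeding".
- Transfusion: "transfusion for overt bleeding".
- A procedure or operation to stop the bleeding, leaving skin stitches and pressure dressings out of account.
- Intravenous vasoactive drugs given for the bleed.
- Death: "probable or definite fatal bleeding".

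The composite has two further routes by which a bleed could be counted. One is device-related readmission or a lengthened stay. The other is a discretionary clause. Appendix 1 words that clause as "any Amplifi System-related complication determined to be an Amplifi System-related major complication by both an Investigator and the CEC", whereas the Synopsis and Section 4.5 give the second party as the Medical Monitor ("major complication by both an Investigator and the Medical Monitor").

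**The concern.** A hemoglobin criterion in a bleeding definition lets severity be recognised from a laboratory value, whatever treatment was given. Here the value has a ceiling as well as a floor. Between 3 and 5 g/dL a bleed counts on hemoglobin alone. Above 5 g/dL it counts only if a treatment was given or the Subject died. Of two bleeds managed in the same way, the larger can be classed as not major and the smaller as major.

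What is at stake is the count of one named safety component in a study that aims to confirm that major complications stay acceptable (Section 4.1). Apixaban is the one anticoagulant that the exclusion criteria allow during treatment, Section 7.5 refers to Subjects continuing it, and bleeding is on the list of potential events in Section 12.2.6.

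**Working it through.** The protocol gives no figure for this point to reproduce. The check applies the definition as a rule and then traces where an excluded bleed could still be counted.

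**1. The rule.** Let d be the related drop in hemoglobin (g/dL) with overt bleeding. As written:

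major bleeding = (3 ≤ d ≤ 5) or transfused or procedure/surgery or IV vasoactive drug or fatal.

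Set the last four to no, so that only d decides:

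| d (g/dL) | As written | With d ≥ 3 |
|---|---|---|
| 2.9 | no | no |
| 3 | yes | yes |
| 4 | yes | yes |
| 5 | yes | yes |
| 5.1 | no | yes |
| 6 | no | yes |
| 7 | no | yes |

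The classification turns from yes back to no as the bleed gets larger.

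**2. Could the range be a loosely written minimum?** The text does not say so. In the same appendix, major thrombocytopenia has a one-sided platelet limit (51,000 per microliter or lower), so one-sided limits are written as such where they are meant. No other section gives a hemoglobin threshold for major bleeding.

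**3. Can a Subject reach the gap?** Entry excludes hemoglobin below 10 g/dL and sets no upper limit (Section 4.6). A drop above 5 g/dL leaves a value below the starting value minus 5:

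- start 10: below 5
- start 11: below 6
- start 12: below 7
- start 13: below 8

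The gap is implausible near the entry floor and more plausible at higher starting values. As an assumed illustration (the protocol gives no baseline distribution), take a start of 13.5:

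- 13.5 − 8.0 = 5.5 g/dL, outside the range
- 13.5 − 10.0 = 3.5 g/dL, inside the range

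The procedure criterion would not rescue a bleed stopped with skin stitches or a pressure dressing, because it excludes both.

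**4. What happens in the composite?** A bleed that misses all five criteria can still enter the composite in two ways:

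- **Hospitalization.** Appendix 1 defines a prolonged stay as any lengthening of the admission due to a device-related complication, with no severity floor. Subjects are inpatients until the device is out (Section 7.0).
- **The discretionary clause.** This needs two parties to agree. The second is the CEC in Appendix 1 and the Medical Monitor in the Synopsis and Section 4.5. Section 15.5 sets up an Independent Safety Board and a Medical Monitor and does not mention a CEC.

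By either route the event is recorded as a hospitalization or an otherwise major complication, not as major bleeding.

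**5. Size of one event.** With ten Subjects, 1/10 − 0/10 = 10 percentage points. Exact (Clopper-Pearson) 95% intervals, for illustration only because the protocol plans none for safety rates:

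- 0/10: upper limit 1 − 0.025^(1/10) = 30.8%, so 0 to 30.8%
- 1/10: lower limit 1 − 0.975^(1/10) = 0.25%, so 0.25% to 44.5%

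**The case against.** The strongest reply is that the gap is narrow and well backed up. To be missed by the composite, a bleed must exceed 5 g/dL, be non-fatal, and be managed without transfusion, procedure, surgery or vasoactive drugs. It must also cause no readmission or longer stay, and not be judged major by the two parties named. Most bleeds that large would probably be caught somewhere on that path. The study is not powered (Section 14.1), safety is summarised descriptively, and adverse events are also reported by type with severity and relatedness (Section 14.2.3). Such a bleed would therefore be visible among at most ten Subjects, and no decision rule turns on the count. Ten percentage points is what any single event is worth at this size and is not specific to this defect.

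All of that stands as a limit on the consequence, and it rules out two stronger readings that a reader might infer:

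- **That the Subject is lost from the main safety measure, or that the composite rate is wrong.** The documents do not support this, because the hospitalization component and the discretionary clause may both count the event.
- **That the definition drops its most severe bleeds.** It does not. Fatal bleeds and those needing surgery, a procedure or vasoactive drugs are all kept. What is missing is one band that rests on hemoglobin alone.

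The reply does not remove the defect. Entry through another route leaves the major-bleeding component short by one. It also makes capture depend on how the bleed was managed, or on a judgement whose second party is named inconsistently.

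**Conclusion.** The point holds as a defect in the definition of one component. Read literally, a related overt bleed with a drop above 5 g/dL is not major bleeding unless one of the four other criteria applies, while a drop of 3 to 5 g/dL is. Each such event would take one Subject, 10 percentage points at n = 10, from the major-bleeding component. Whether the composite also changes depends on the hospitalization component and the discretionary clause, and it may well not change.

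The conclusion rests on reading the range as written. How often the case would arise cannot be computed from the protocol. It is judged uncommon, since most bleeds of this size would probably be transfused or otherwise treated. The correction is worth making before events are classified, because the wording is wrong and costs little to put right.

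**What to change.** In Appendix 1, replace the two-sided range in the hemoglobin criterion for major bleeding with a single lower limit, a drop of at least 3 g/dL. Keep the requirements that the bleeding be overt and that the drop be related to it. This keeps the sponsor's own lower threshold and changes only how an event is classified, not how a Subject is managed.

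In the same edit, reconcile the second party in the discretionary clause, so that Appendix 1 agrees with the Synopsis and Section 4.5.

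The cost is a few words in one definition. The blood count is already taken at baseline, before placement, daily during treatment, after removal, and at weeks 1, 2 and 6 (Section 8.4), so no test is added. The only downside is a possibly higher count of major bleeding.

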### **Exclusion Criteria**

- 1) Known allergy to Amplifi System components (polyurethane, nitinol), iodinated contrast agents, heparin, or apixaban
- 2) Known or suspected active infection at the proposed time of Amplifi System placement
- 3) Known bleeding diathesis, including from uncorrected coagulopathy
- 4) Known thrombophilia, requiring treatment
- 5) Hb  $<10$  gm/dL
- 6) Platelet level  $< 100,000 /mm^3$
- 7) Need for continued treatment with anti-platelet agents or other anticoagulants (other than apixaban) during the Amplifi System treatment period
- 8) Known history of patent foramen ovale  $\geq 2$  mm
- 9) History of recent intracranial or gastrointestinal bleeding
- 10) Documented recent central venous or right atrial thrombus
- 11) Known presence or recent history of intracranial or gastrointestinal bleeding or presence of underlying conditions that would predispose to intracranial or internal bleeding. Documented recent central venous or right atrial thrombus
- 12) History of recent ipsilateral central venous occlusion, stenosis  $\geq 50\%$ , angioplasty, or stent placement
- 13) Pregnancy, lactation, or plans to become pregnant during the Study

- 14) Unwillingness or inability to comply with procedures specified in the Protocol, or difficulty or inability to return for follow-up visits as specified by the Protocol
- 15) Participation in any other investigational drug or medical device study that has not completed primary endpoint evaluation or clinically interferes with the endpoints from the Study, or planned future participation in such studies prior to the completion of the Study

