- *Intracranial bleeding* is defined as any bleeding within the intracranial vault, including bleeding in the brain parenchyma and meningeal spaces.
- *Pseudoaneurysm of Study AVF* is defined as a locally contained hematoma of a Study AVF outflow vein with persistent blood flow in the hematoma and a neck between the hematoma and the Study AVF outflow vein that does not close spontaneously that is located between the Study AVF anastomosis and the axilla that requires treatment with an interventional

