**Table 6: Publications Relevant to Safety and Effectiveness – Extracorporeal Blood Pumps**

Publication	Overview	Safety Data
Thomas, et al. "Bleeding and Thrombotic Complications in the Use of Extracorporeal Membrane Oxygenation Semin Thromb Hemost. 2018 Feb;44(1):20-29. doi: 10.1055/s-0037-1606179. Epub 2017 Sep 12.	Section of Pediatric Critical Care Medicine, Department of Pediatrics, Baylor College of Medicine, Texas Children's Hospital, Houston, Texas. Division of Transfusion Medicine and Coagulation, Department of Pathology and Immunology, Baylor College of Medicine, Texas Children's Hospital, Houston, Texas.	Extracorporeal membrane oxygenation (ECMO) has been used for >40 years to support lung and heart failure; however, bleeding and thrombosis remain serious complications. The known etiologies of bleeding include heparin effect or overdose, coagulopathy, thrombocytopenia, platelet dysfunction, acquired von Willebrand syndrome, and hyperfibrinolysis. Bleeding sites may include cannula insertion sites, recent surgical incisions, vascular access sites, lung, gastrointestinal tract, mouth, nose, thoracic cavity, abdominal cavity, and brain. Massive bleeding in the brain, the most feared bleeding complication, can be rapidly fatal because it occurs in a rigid closed space, is difficult to drain, and cannot be stopped with direct pressure to the bleeding site. Pulmonary hemorrhage may cause irreversible lung damage. Management should be swift and precise to prevent fatal

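### The major-bleeding definition has no intracranial limb, so a conservatively managed, non-fatal intracranial bleed can reach the safety composite only through indirect limbs (minor)

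*Protocol*

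**What the plan says.** The main safety measure (Protocol Synopsis and Section 4.5) is the rate of Major Device-Related Adverse Events, from implantation to 30 days after device removal and AVF creation. Device-related major bleeding is one named component. Appendix 1 defines it by any one of five limbs:

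1. "overt bleeding plus a drop in hemoglobin of 3 to 5 g/dL wherein the hemoglobin drop is related to the bleeding"
2. "transfusion for overt bleeding"
3. "bleeding requiring an interventional procedure or surgery for control (not including the placement or removal of skin sutures or pressure dressings")
4. "the administration of intravenous vasoactive agents for overt bleeding"
5. "probable or definite fatal bleeding"

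Appendix 1 also has an entry for intracranial bleeding, which "is defined as any bleeding within the intracranial vault, including bleeding in the brain parenchyma and meningeal spaces". In the body of the protocol the term is used only for eligibility, in exclusion criteria 9 and 11. Criterion 11 also bars the "presence of underlying conditions that would predispose to intracranial or internal bleeding".

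On anticoagulation, exclusion 7 exempts apixaban from the bar on continued anticoagulants, and Section 7.5 has Subjects remain on it after a pump stoppage.

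**The concern.** A hemoglobin drop, a transfusion or a procedure for control are reasonable markers of serious bleeding when the harm comes from blood loss. Intracranial bleeding harms by its location. It may be invisible externally, may barely change hemoglobin, and may be managed by observation. The definition therefore fits poorly with the one bleeding site that the protocol takes care to define and to screen for.

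Two things are at stake. The first is the label: a minor ooze that is transfused is major bleeding, while an intracranial bleed managed conservatively is not. The second is whether the event enters the composite at all, because it must then qualify through a limb not written for bleeding. The stated objective in Section 4.1 is to confirm that major complications stay within an acceptable range, so both the composite and its make-up will be read closely.

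**Working it through.** This is mainly a check of wording. The protocol gives no figure to reproduce.

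**Step 1: test case.** Take a device-related, non-fatal intracranial bleed with no related hemoglobin drop of 3 to 5 g/dL, no transfusion, no interventional procedure or surgery, and no intravenous vasoactive agent. Against the five limbs of Appendix 1:

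- Limb 1 (overt bleeding with hemoglobin drop): not met. It also requires the bleeding to be overt, a term Appendix 1 does not define.
- Limb 2 (transfusion): not met. It also requires overt bleeding.
- Limb 3 (procedure or surgery): not met.
- Limb 4 (vasoactive agents): not met. It also requires overt bleeding.
- Limb 5 (fatal): not met.

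The event is not major bleeding. If any one of the four absent features were present (with the bleeding judged overt for limbs 1, 2 and 4), it would be.

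**Step 2: comparison within Appendix 1.** Major air embolism can qualify by clinical consequence, including stroke. Major bleeding has no consequence-based limb short of death and no site-based limb.

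**Step 3: other routes into the composite (Section 4.5).**

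- Death, major surgery and major interventional procedure: not met in the test case.
- Prolonged or repeat hospitalization: likely met. Appendix 1 sets no severity threshold, and Section 7.0 keeps Subjects in hospital until the device is removed.
- Catch-all: possible, but it needs two parties to agree. Section 4.5 and the Synopsis name the Investigator and the Medical Monitor. Appendix 1, to which Section 4.5 refers for the detailed definition, names the Investigator and the CEC. CEC is not in the abbreviation list, and Section 15.5 sets up only an Independent Safety Board with a Medical Monitor.

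**Step 4: relatedness.** Every limb requires device-relatedness. The relational criteria in Section 12.2 allow an event to be called unrelated where there is evidence of a potential alternative cause such as concurrent medication, and apixaban could be cited.

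**Step 5: size, as illustration only.** Exact (Clopper-Pearson) 95% intervals at n = 10:

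- 0/10: lower limit 0; upper limit 1 − 0.025^(1/10) = 30.8%.
- 1/10: lower limit 1 − 0.975^(1/10) = 0.3%; upper limit solves (1 − p)^10 + 10p(1 − p)^9 = 0.025, giving 44.5%.

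These describe the bleeding component alone. If the hospitalization or catch-all limb is met, the composite is 1/10 under either definition.

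**The case against.** The strongest reply is that the event is very likely to be counted. The planned measure is the composite, no separate major-bleeding rate is listed, and an intracranial bleed in an inpatient would almost certainly lengthen the stay or, after discharge, lead to readmission. It would also be a serious adverse event if it were life-threatening, permanently disabling or prolonged the stay, and Section 14.2.3 reports such events by type with numbers and percentages of Subjects. This stands, and it is why the point is minor.

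Two stronger readings are tempting. A reader might infer that only an operation, a transfusion or vasoactive agents would make such a bleed major. The text does not support that: the hemoglobin limb also applies, and limb 3 covers any interventional procedure for control. A reader might also infer that the event disappears from the main safety measure and biases the result towards the device. The hospitalization limb makes that unlikely, and the documents give no incidence of intracranial bleeding with this device. Section 3.2.3 reports no major bleeding in the ten earlier Subjects.

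The supporting evidence also has limits. Gastrointestinal bleeding is likewise defined in Appendix 1 and used only for eligibility, so a glossary entry does not prove that a limb was forgotten. Appendix 2, Table 6 says "Massive bleeding in the brain, the most feared bleeding complication, can be rapidly fatal because it occurs in a rigid closed space", but that concerns massive bleeding during ECMO, and fatal bleeding is already limb 5. Several other major-event definitions also rely on treatment given, such as a chest tube or thrombectomy. So this is a weakness in a design choice. It is not a contradiction in the text, except for the catch-all adjudicator, which does conflict.

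**Conclusion.** The gap is real and small. As written, a non-fatal, device-related intracranial bleed without the hemoglobin drop or any of the listed treatments is not major bleeding. Its main effect is a mislabelled component. The risk of a missed composite event is small: it arises only if hospitalization is not judged prolonged or repeated and the catch-all is not invoked, and the catch-all is weakened by having two different adjudicators.

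This rests on reading the five limbs literally, on the bleed being judged device-related, and on Subjects being anticoagulated with apixaban, as exclusion 7 and Section 7.5 imply. In an unpowered, descriptive study of up to ten Subjects (Section 14.1) no test or decision rule depends on it. Severity: minor.

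**What to change.** Add one limb to the definition of Amplifi System-related major bleeding in Appendix 1: *device-related intracranial bleeding (as defined in this Appendix), confirmed by imaging, regardless of hemoglobin change or treatment*. Carry it into the adjudication form.

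Name the same catch-all adjudicator in the Synopsis, Section 4.5 and Appendix 1. The Medical Monitor is the only one of the two whose adjudication role is set out in Section 15.5.

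The cost is one line of text, one correction and a form update. No visit, procedure or treatment changes. The downside is that an incidental or asymptomatic intracranial finding judged device-related would count as major, so the reported count could be slightly higher. The change does not settle relatedness, which the new limb would still require.

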## Clinical Protocol

### FIH-3

Doc No: CLINP1837  
Revision: D  
DCO No: 25-009  
Effective Date: 02/06/25

system during the placement, operation, use, or removal of the Amplifi System that is not due to a cause other than the placement, operation, use, or removal of the Amplifi System; wherein the air embolism is documented by imaging and:

- results in air embolism-related hypotension, arrhythmia, hemodynamic instability, paradoxical embolization, myocardial infarction, stroke, mesenteric ischemia, or death;
- requires a procedure or surgery to remove the air that forms after air embolism; or
- requires a thrombectomy procedure or surgery, thrombolytic therapy, or long-term anticoagulation to remove thrombus that forms after air embolism.
- *Amplifi System-related major thrombosis* is defined as the formation of thrombus in an artery, vein, or the right atrium due to the placement, operation, use, or removal of the Amplifi System, wherein the thrombosis is documented by imaging and the Subject requires a thrombectomy procedure or surgery, thrombolytic therapy, or long-term anticoagulation; not inclusive of a thrombectomy procedure or surgery that occurs during the creation of the Subject AVF.
- *Amplifi System-related major thromboembolism* is defined as thromboembolism in the arterial or venous system due to the placement, operation, use, or removal of the Amplifi System, wherein the thromboembolism is documented by imaging and the Subject requires a thrombectomy procedure or surgery, thrombolytic therapy, or long-term anticoagulation; not inclusive of a thrombectomy procedure or surgery that occurs during the creation of the Subject AVF.
- *Amplifi System-related major hemolysis* is defined as hemolysis documented by laboratory testing during the Amplifi System treatment period that is not due to a cause other than the placement, operation, use, or removal of the Amplifi System, and requires blood transfusion and/or results in thrombotic events, multiple organ failure and mortality.
- *Amplifi System-related major thrombocytopenia* is defined as a platelet level of  $\leq 51,000$  per microliter during the Amplifi System treatment period that is not due to a cause other than the placement, operation, use, and removal of the Amplifi System, and requires transfusion.
- *Amplifi System-related re-hospitalization* is defined as an admission to a hospital due to an Amplifi System-related complication, not inclusive of a visit to an emergency room, clinic, or outpatient facility that does not result in admission to a hospital.
- *Amplifi System-related prolonged hospitalization* is defined as a prolongation of a hospital admission due to an Amplifi System-related complication.
- *Amplifi System-related major surgery* is defined as an open surgery involving an incision and the cutting of the body to address a life-threatening adverse event, to prevent disability, or to treat or prevent permanent impairment or damage to a vital body structure or function due to an Amplifi System-related complication; not inclusive of the placement of pressure dressings, the placement or removal of skin sutures, the creation of an AVF or AVG, or the placement or removal of a hemodialysis catheter.
- *Amplifi System-related major interventional procedure* is defined as an interventional procedure to address a life-threatening adverse event, to prevent disability, or to treat or prevent permanent impairment or damage to a vital body structure or function due to an

